#### **13.4.3. Dosing Interruptions**

If multiple days of dosing are missed due to subject error, the participant may resume QD dosing for 3 days under PI discretion before returning to the BID regimen. If less than 2 days (4 consecutive doses) are missed, the subjects should resume the BID regimen.

If study medication is missed for  $\geq 7$  consecutive days, for any reason, the decision to resume should be based on discussion between the PI and Sponsor Clinical Director.

All dosing interruptions should be documented in the case report forms.

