#### **Primary Estimand**

For the primary endpoints, the primary estimand for the percentage change from baseline in body weight is defined as the average treatment effect of K-757 alone and the combination of K-757 + K-833 relative to placebo in the mITT analysis population, had they remained on their randomized treatment for the entire planned duration of the trial (“hypothetical” estimand).

A mixed model for repeated measurements (MMRM) analysis will be applied with gender, treatment, visit and treatment-by-visit interaction as fixed effect and baseline body weight as a covariate. The MMRM model will use assessments only from participants who are taking the randomized treatment until end of treatment or until first discontinuation of randomized treatment. An unstructured covariance will be used. If the unstructured covariance structure leads to nonconvergence, Akaike’s information criteria will be used to select the best covariance structure.

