#### **Criteria for considering resumption of IMP after interruption:**

If any of these criteria for interruption of IMP are met, dosing may **not** resume unless/until all the following criteria are met:

1. Another etiology for the abnormal liver biochemistries leading to IMP interruption (e.g., active hepatitis with specific etiology demonstrated, cholecystitis, biliary obstruction) is established **and**
2. Liver biochemistries have normalized or returned to  $\sim$  baseline for  $\geq 2$  weeks **and**
3. The participant is able and willing to undergo close observation after resumption of IMP **and**
4. Both the investigator and the Sponsor medical monitor agree that resumption of IMP is appropriate.

Close observation must be initiated at the resumption of IMP. Close observation may stop if liver biochemistries have remained normal or at  $\sim$ baseline for  $\geq 2$  weeks **and** both the investigator and the Sponsor medical monitor agree this is appropriate.

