#### 5.1.6 Analysis Visit Windows

For body weight, hemodynamic data (systolic blood pressure, diastolic blood pressure and heart rate) and lab measures (total cholesterol, LDL, HDL, and triglycerides), unscheduled visits and end of treatment visits and follow-up visits for participants who discontinued study drug earlier will be mapped based on analysis visit window below. The analysis visit windows will be exhaustive so that all available values obtained from unscheduled visits, end of treatment visits and follow-up visits for participants who discontinued study drug earlier have the potential to be summarized. No analysis visit windows will be applied for the study scheduled visits.

For other safety measures, analysis visit windowing will not be applied. The visits and time points reported on the electronic case report form (eCRF) will be used.

The following analysis visit windows will be used to map the unscheduled visits, end of treatment visits and follow-up visits for participants who discontinued study drug earlier of body weight.

Visit	Target Day	Analysis Visit Window Based on Study day
Baseline	1	1
Week 4	29	[2, 43]
Week 8	57	[44, 74]

Week 13 for Participants Discontinued Treatment	92	[75, 95]
Week 13 for Participants Completed Treatment	92	[75, Last Dose Date +3]
Week 15 for Participants Discontinued Treatment	105	>95

The following analysis visit windows will be used to map the unscheduled visits, end of treatment visits and follow-up visits for participants who discontinued study drug earlier hemodynamic data (systolic blood pressure, diastolic blood pressure and heart rate).

Visit	Target Day	Analysis Visit Window Based on Study day
Baseline	1	1
Week 1	8	[2,11]
Week 2	15	[12,18]
Week 3	22	[19,25]
Week 4	29	[26, 36]
Week 6	43	[37, 50]
Week 8	57	[51, 64]
Week 10	71	[65, 81]
Week 13 for Participants Discontinued Treatment	92	[82, 95]
Week 13 for Participants Completed Treatment	92	[82, Last Dose Date +3]
Week 15 for Participants Discontinued Treatment	105	>95

In the event of multiple measurements of the same test in the same window, if the measurements are from different visit categories, the priority order is scheduled visit, end of study visits and follow-up visits, then unscheduled visit. For the measurements in the same visit category, the value measured nearest to the target day will be used; if they are at the same distance to the target day, the latest one will be used.

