#### 5.8.1.1 Primary Estimand

**Primary trial objective**: To assess relative (%) change from baseline in body weight after 13 weeks of treatment with K-757 alone and in combination with K-833, in comparison to placebo

**Estimand Scientific Question of Interest**: What is the effect on body weight of assigning participants to K-757 alone and in combination with K-833, in comparison to placebo on treatment?

- Variable: % change in body weight
- Analysis Set: Modified intent-to-treat set
- Analysis time point: 13 weeks post-baseline
- Treatment: Average treatment effect of K-757 alone and in combination with K-833 relative to placebo
- Analysis methodology: Mixed model for repeated measures (MMRM)

- Intercurrent events: Treatment discontinuation All available data at Week 13 had participants remained on their randomized treatment for the entire planned duration of the trial are used in the analysis ("hypothetical" estimand).
- Missing data: Missing data is imputed using MMRM based on missing at random (MAR) assumption at Week 13.

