#### 5.8.1.2 Primary Analysis

A mixed model for repeated measurements (MMRM) analysis will be applied with gender, treatment, visit and treatment-by-visit interaction as fixed effect, and baseline body weight as a covariate. The MMRM model will use assessments only from participants who are taking the randomized treatment until end of treatment if they complete treatment or until 3 days after discontinuation of randomized treatment; scheduled follow up assessment will also be included in analysis. An unstructured covariance will be used. If the unstructured covariance structure leads to nonconvergence, other covariance structures, such as, compound symmetry (CS) and autoregressive (AR(1)) will be used. Akaike's information criteria will be used to select the best covariance structure.

The least squares (LS) means, difference in LS mean (K757 vs placebo, K-757+K-833 vs placebo), the corresponding 95% CI and the p-value will be provided. In addition, descriptive statistics including number of participants, mean and standard error will be provided.

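### The primary on-treatment rule is tied to completion or formal discontinuation rather than to days since the last dose, so some off-drug weights enter the hypothetical-estimand MMRM.

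*SAP*

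**What the plan says.** Protocol 16.6.1 defines the primary estimand as the effect in the mITT population "had they remained on their randomized treatment for the entire planned duration of the trial", and uses weights "until end of treatment or until first discontinuation of randomized treatment".

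SAP 5.8.1.1 lists one intercurrent event: "Intercurrent events: Treatment discontinuation All available data at Week 13 had participants remained on their randomized treatment for the entire planned duration". SAP 5.8.1.2 then gives the data rule, first for those who complete: "The MMRM model will use assessments only from participants who are taking the randomized treatment until end of treatment if they complete treatment". For those who stop early, the same sentence sets a second limit: "or until 3 days after discontinuation of randomized treatment; scheduled follow up assessment will also be included in analysis". The 3-day extension and the follow-up clause are not in the protocol rule, although SAP section 8 reports no changes from the protocol.

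The protocol treats interruption as a state distinct from discontinuation, with resumption possible:

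- Protocol 13.4.3, once at least 7 days have been missed: "consecutive days, for any reason, the decision to resume should be based on discussion between the PI and Sponsor Clinical Director". No maximum length is given.
- Protocol 8.3.1.1: dosing is interrupted on suspicion of pancreatitis and resumed if it is ruled out.
- Protocol Appendix A, among the conditions for resuming after a liver-test interruption: "Liver biochemistries have normalized or returned to" about baseline for at least 2 weeks.

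On visit timing, SAP 5.1.6 states "No analysis visit windows will be applied for the study scheduled visits". Its body-weight table nevertheless has a Week 13 row for participants who completed treatment, running from Day 75 to 3 days after the last dose. SAP 4.5 and 5.8.1.4 exclude completers whose Week 13 weight came more than 3 days after the last dose, but only from the per-protocol (completer) analysis.

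**The concern.** A hypothetical estimand needs a data rule that separates weights on drug from weights off drug. Here the rule depends on a status, completed or discontinued. A participant in the middle of an interruption has neither status, so no limit applies and the weight counts as if dosing had continued. For completers, the 3-day standard that the SAP uses elsewhere is not clearly applied to the scheduled Visit 12, which supplies the primary endpoint. For participants who stop, the follow-up clause may undo the 3-day limit in the sentence that sets it.

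At stake is whether the primary number answers the stated question, and whether two programmers working from SAP 5.1.6 and 5.8.1.2 would select the same weights. On-treatment post-baseline weights are scheduled only on Days 29, 57 and 92, so one misclassified weight is a third of a participant's on-treatment data. The secondary weight endpoints (SAP 5.8.2.1 and 5.8.2.2) use the same model and inherit the rule.

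**Working it through.** **1. The plan's own figure.** Inputs from Protocol 16.2 and SAP 3.4: 150 randomized 1:1:1, difference 4, SD 4, 20% dropout, two-sided alpha 0.05.

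- n per arm = 50 × 0.80 = 40
- SE = 4 × √(2/40) = 0.894
- 4/0.894 − 1.96 = 2.51, giving power of 99.4% (99.3% by noncentral t)

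The stated figure of more than 95% is correct.

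**2. Visit 12 timing.** The last dose is the evening of Day 91, and Visit 12 is Day 92 ± 3 (Protocol Table 2), so Days 89 to 95.

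- Day 94: 94 − 91 = 3 days off drug
- Day 95: 95 − 91 = 4 days off drug

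Day 95 meets the visit schedule but fails the 3-day limit.

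**3. How each weight is handled.**

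| Weight | Primary MMRM (SAP 5.8.1.2) | Per-protocol set (SAP 4.5, 5.8.1.4) |
|---|---|---|
| Day 29 or 57, during an interruption later resumed | Kept; neither limit has been reached | Participant kept if compliance is at least 80% and the Week 13 weight qualifies |
| Scheduled Visit 12 on Day 95, completer | Kept under the scheduled-visit exemption; the completer row in SAP 5.1.6 points the other way | Excluded |
| Scheduled follow-up after a permanent stop | May be kept under the follow-up clause | Participant not in the set |

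**4. What the follow-up clause could do.** Follow-up is about 14 days after the last dose (Protocol 7.1). For participants who discontinued, SAP 5.1.6 maps Days 75 to 95 to Week 13. A last dose on Days 61 to 81 puts the follow-up on Days 75 to 95 (61 + 14 = 75; 81 + 14 = 95). If the clause admits that visit, a weight about 14 days off drug could serve as a Week 13 value.

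**5. Whether the completer analysis is a backstop.** SAP 5.7.2 divides days with complete dosing by actual dosing days. Over 91 planned days, with dosing otherwise complete:

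- 14-day gap: 77/91 = 84.6%
- 21-day gap: 70/91 = 76.9%
- 28-day gap: 63/91 = 69.2%

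If actual dosing days leave out the gap, all three become 100%. Under either denominator, a 14-day gap passes the 80% threshold.

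**6. Size, by assumption only.** No interruption rate appears in the documents. Shrinkage = share of active Week 13 weights affected × share of effect lost × 4.

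- 0.05 × 0.25 × 4 = 0.05 points (difference 3.95, power 99.3%)
- 0.10 × 0.50 × 4 = 0.20 points (difference 3.80, power 98.9%)
- Extreme corner: 0.20 × 1.00 × 4 = 0.80 points (difference 3.20, power 94.7%)

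Against an SE of 0.894, the first two are about 6% and 22% of one standard error.

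**7. Precision cost of dropping such weights.** If 5% or 10% of one active arm's Week 13 values are set to missing, n falls from 40 to 38 or 36:

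- √[(1/38 + 1/40)/(2/40)] = 1.013
- √[(1/36 + 1/40)/(2/40)] = 1.027

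The SE rises by about 1.3% to 2.7%, before the MMRM recovers information from earlier visits.

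**The case against.** The sponsor has several fair replies.

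- *The wording about participants taking the randomized treatment already excludes interruption weights.* This reading is possible, but the sentence gives only completion and discontinuation as end points.
- *A gap still open at Visit 12 cannot be followed by resumption, so that participant has not completed.* This is reasonable, and it moves the clearest interruption cases to Days 29 and 57, whose weights reach the Week 13 contrast only indirectly. It does not settle when the 3-day clock starts: discontinuation is not defined as the last dose date, and SAP 5.11.1.2 uses the two dates as separate terms.
- *The completer row in SAP 5.1.6 already sets a limit.* A reader should not infer that completers have no limit anywhere. The row and the scheduled-visit exemption conflict. Within the visit window the disagreement is one day (Day 95); a later Visit 12 would be a protocol deviation.
- *Treating brief gaps as part of the assigned regimen is legitimate.* It is, but the SAP should then say so, because its estimand is worded as continued treatment.

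Three stronger inferences are tempting and are not supported. First, Protocol 5.4 says that the satiety effect follows hormone concentration closely; it says nothing about how fast body weight returns. Second, more interruptions on active drug is plausible given the expected GI intolerance, but no rate is given, and liver-test interruptions that resume are those for which another cause was established. Third, it cannot be said that a weight 4 days after a permanent stop is always excluded, because the follow-up clause may admit it.

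**Conclusion.** The point holds as a gap and an internal conflict in the primary data rule. Followed as written, SAP 5.8.1.2 places weights taken during interruptions, and a Day 95 Visit 12, into an estimand defined by continued treatment. The follow-up clause may add weights from participants who stopped. Day 95 needs no assumption about behaviour: SAP 5.1.6 and 5.8.1.2 retain a weight that SAP 4.5 and 5.8.1.4 reject.

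The numerical effect is probably small. The 0.05-0.20 point shrinkage rests on assumed shares, and its direction assumes that the affected weights fall in the active arms. A reader might infer that the trial is underpowered; the documents do not support that. Power stays at about 99% over that range and falls slightly below 95% only if 20% of active weights lose the whole effect. The change is still worth making before database lock, because it concerns the primary analysis and the planned completer analysis may not detect the affected participants.

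**What to change.** In SAP 5.8.1.2, state that a weight, scheduled or not, informs the Week 4, 8 and 13 on-treatment estimates only if taken no more than 3 days after the most recent dose actually taken, using the dosing dates and interruptions in the eCRF. Otherwise treat it as missing for the hypothetical estimand and keep it for the treatment-policy estimand. In addition:

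- Name interruption as an intercurrent event in SAP 5.8.1.1.
- Reconcile SAP 5.1.6 with 4.5 and 5.8.1.4 so that a Day 95 weight has one stated handling per analysis.
- Delete the follow-up clause from the primary analysis, or restrict it to a separate Week 15 visit that cannot supply a Week 13 value.
- Record the departures from the protocol rule in SAP section 8.

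The cost is SAP wording and one derivation from data already collected (Protocol 13.4.3 and 13.7). A few Week 4, 8 or 13 weights are lost, with the SE up about 1-3% under the 5-10% assumption. Reliance on missing at random rises slightly. If the follow-up clause is deleted, Week 15 weights leave the primary model altogether, which could be up to one per participant. The rule does not remove weights taken soon after dosing resumes; a sensitivity analysis can examine those.

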### **8.3. Subject Withdrawal Criteria**

#### **8.3.1. Procedures for Discontinuation or Withdrawal of a Subject**

##### **8.3.1.1. Discontinuation of Trial Treatment**

Discontinuation of trial product can be decided by either the investigator or the subject. A participant may discontinue his or her participation without giving a reason at any time during the trial.

Participants who discontinue trial product should continue with the scheduled visits and assessments to ensure continued counselling and data collection.

If the subject does not wish to attend the scheduled clinic visits, efforts should be made to have the visits converted to phone contacts. However, all efforts should be made to have the subject attend at least the 'end of treatment' clinic visit containing the final data collection of primary and confirmatory secondary efficacy endpoints, and the 'end of trial' visit.

The 'end of trial' visit is scheduled approximately 2 weeks after the final data collection, to ensure the safety of the subject. If the subject has discontinued trial product >2 weeks prior to the 'end of treatment' visit, and the requirements for the follow-up period prior to the 'end of trial' visit is fulfilled, then the 'end of trial' visit can be performed in combination with 'end of treatment' visit.

If the subject refuses to attend the 'end of treatment' and/or 'end of trial' visit, information about the attempts to follow up with the subject must be documented in the subject's medical record.

The subject must be discontinued from trial product if any of the following applies:

1. Safety concern as judged by the investigator
2. Pregnancy
3. Intention of becoming pregnant
4. Liver function test (LFT) abnormalities meeting specified discontinuation criteria (refer to [Appendix A](#) for discontinuation criteria and instruction on management of LFT abnormalities)
5. Confirmed pancreatitis (see below)

If acute pancreatitis is suspected based on clinical signs and symptoms, blinded study medication should be interrupted immediately, and appropriate diagnostic assessments should be performed.

- A diagnosis of acute pancreatitis requires at least 2 of the following 3 findings :
  - abdominal pain consistent with acute pancreatitis (persistent, severe epigastric pain, frequently radiating to the back); abdominal pain is often associated with nausea and vomiting.
  - serum lipase and/or amylase activity  $\geq 3X$  the laboratory ULN

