#### 3 Study Design

#### 3.1 Overall Study Design

This is a randomized, double-blind, placebo-controlled 13-week study to evaluate the efficacy of K-757 alone and in combination with K-833 versus placebo in participants who are obese without type 2 diabetes mellitus (T2DM). Approximately 150 participants will be enrolled and randomized 1:1:1 to receive K-757 alone, K-757 + K-733, or matching placebos (Figure 1 and Table 1)

Figure 1: Study Schematic

<sup>a Screening will occur over approximately 4 weeks.

The study will be comprised of a Screening period (up to 28 days prior to the treatment period), a 13-week double-blind Treatment Period (dosing on Days 1 to 91; end-of-treatment visit Day 92), and a post-study Follow-Up period (approximately 14 days after their last dose). The total duration of the study for each participant will be up to approximately 19 weeks. Randomization

<sup>b Refer to the Dosing Table and Section 5.4.1 of the Clinical Study Protocol (CSP) for study drug administration details.

<sup>c Week indicates the duration of treatment completed prior to the visit, not the week in which the visit occurs. For example, "Week 1" visit is targeted to occur on Day8 (the first day of the 2nd week of treatment).

will be stratified by gender (male/female). Enrollment into each gender strata will be capped at 70% (i.e., neither gender may exceed 70% of total enrollment).

**Table 1:** Dosing Table

				W	eek	
Arm	Time (AM/PM)		Week 0 (D1-7)	Week 1 (D8-14)	Week 2 (D15-21)	Week 3 (D22-28)
W 757   W 922	AM	757/833 (mg)	30/100	30/100	60/100	120/100
K-757+K-833	PM	757/833 (mg)	pbo/pbo	30/100	60/100	120/100
K-757 alone	AM	757/833 (mg)	30/pbo	30/pbo	60/pbo	120/pbo
K-757 alone	PM	757/833 (mg)	pbo/pbo	30/pbo	60/pbo	120/pbo
Placebo to K-	AM	757/833 (mg)	pbo/pbo	pbo/pbo	pbo/pbo	pbo/pbo
757 and K-833	PM	757/833 (mg)	pbo/pbo	pbo/pbo	pbo/pbo	pbo/pbo

For additional titration information, see Section 5.4.1 of the CSP

Participants will return to the trial site at the times described in the study schematic and schedule of assessments (SOA) (Table 2) to complete study procedures. During two of the on-treatment weeks when participants do not return to the trial site, the site will contact the participants by phone in order to assess study medication compliance, new concomitant medication use, and adverse events (AEs).

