#### 4.5 Per Protocol Analysis Set

The per protocol analysis set consist of all participants who completed 13-week treatment and have weight assessment at week 13 and treatment compliance >=80%. Participants who completed treatment but have week 13 assessment done more than 3 days after last dose date and participants whose weights at week 13 are collect at non-fasted state are excluded.

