#### 8 Changes from Pre-specified Analyses in the Protocol

There were no changes in the analyses or definitions planned in the CSP.

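### SAP 5.8.1.2 adds off-drug follow-up weights to the primary on-treatment MMRM without saying whose; if discontinuers' weights are used, the Week 13 difference is likely attenuated

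*SAP*

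**What the plan says.** - **Estimand.** SAP 5.8.1.1 defines a hypothetical estimand: the data that would arise "had participants remained on their randomized treatment for the entire planned duration of the trial".
- **Protocol data rule.** Protocol 16.6.1 (Primary Estimand) admits weights only "until end of treatment or until first discontinuation of randomized treatment". It has no follow-up clause.
- **SAP data rule.** SAP 5.8.1.2 admits weights "until 3 days after discontinuation of randomized treatment; scheduled follow up assessment will also be included in analysis". It does not say whose follow-up is meant.
- **Timing of follow-up.** SAP 3.1 describes a "post-study Follow-Up period (approximately 14 days after their last dose". Protocol 8.3.1.1 asks discontinuers to keep attending scheduled visits. If drug stopped more than 2 weeks before the end-of-treatment visit, the end-of-trial "visit can be performed in combination with" the end-of-treatment visit.
- **Windows.** SAP 5.1.6 says that "end of treatment visits and follow-up visits for participants who discontinued study drug earlier will be mapped based on analysis visit window below". The body-weight windows are Week 4, Days 2 to 43; Week 8, Days 44 to 74; Week 13 for discontinuers, Days 75 to 95; Week 15 for discontinuers, after Day 95.
- **Secondary estimand.** SAP 5.8.1.3 uses retrieved dropouts' data up to Week 15 for the treatment-policy analysis, and says that the handling of discontinuation is all that differs from the primary.
- **Declared changes.** SAP section 8: "There were no changes in the analyses or definitions planned in the CSP".

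**The concern.** The follow-up clause comes straight after the discontinuation rule and carries no restriction. Two programmers could follow it faithfully and deliver different primary results, one using completers' Week 15 weights only and the other using everyone's follow-up weight. The second result would mix the hypothetical and treatment-policy estimands, which SAP 5.8.1.3 separates by exactly this feature.

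Elsewhere the SAP is strict about off-drug weights at Week 13. SAP 4.5 removes from the per-protocol set "Participants who completed treatment but have week 13 assessment done more than 3 days after last dose date".

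The likely direction is attenuation. Protocol 5.4 expects the satiety effect to fade quickly once hormone levels fall, and a person who stops early also loses the remaining weeks of accrual. Protocol 5.3 says the trial is to show whether placebo-adjusted loss is large enough to continue development, so the size of the estimate matters as well as its p-value. The kg-change and 5% responder analyses (SAP 5.8.2) and the subgroup analyses (5.8.3) reuse the same method.

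**Working it through.** **Inputs from the documents.** Difference 4 points, SD 4, two-sided alpha 0.05, 150 randomized 1:1:1, 20% drop-out (SAP 3.4). That is 50 per arm and 50 × 0.8 = 40 after drop-out. Last dose Day 91, end of treatment Day 92, follow-up Day 105.

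**The plan's own power.** SE = 4 × √(2/40) = 0.894. Power ≈ Φ(4/0.894 − 1.96) = Φ(2.51) = 0.994. The stated figure of more than 95% is reproduced.

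**Can a discontinuer's off-drug weight enter, and where?** Let L be the last dose day.

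1. *Follow-up at L + 14.* It falls in Week 4 for L = 1 to 29, in Week 8 for L = 30 to 60, and in Week 13 for L = 61 to 81 (61 + 14 = 75; 81 + 14 = 95). A weight within 3 days of stopping stays in Week 8 while L + 3 ≤ 74, so for L = 61 to 71 no on-treatment early-termination weight competes for Week 13. Example: last dose Day 65, follow-up Day 79.
2. *Combined visit.* With drug stopped more than 14 days before Day 92 (L ≤ 77), one visit at about Day 92 may serve as both, and Day 92 is in the Week 13 window.
3. *Full schedule kept.* Follow-up at about Day 105 is labelled Week 15. Such a person may be many weeks off drug: for L = 30, 105 − 30 = 75 days. Week 13 is missing for that person, so the Week 15 value informs it through the unstructured covariance.

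**Size.** Percent change was simulated with placebo mean −1 and drug effect −4.0 at Day 91 (linear), subject slope SD 3.8 and residual SD 1.2 (SD about 4.0 at Week 13). The model was the maximum-likelihood equivalent of the MMRM, with arm-specific visit means, a common unstructured covariance and covariates omitted, at 40,000 per arm. There were 32 scenarios per follow-up schedule. Results at 20% drop-out in both arms:

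| Weights used | Week 13 difference | Shift |
|---|---|---|
| To last dose + 3 days only | −3.93 to −4.00 | reference |
| Plus completers' Week 15, own visit level | identical | 0.00 |
| Plus discontinuers' follow-up, separate Week 15 level | −3.68 to −3.93 | 0.05 to 0.31 |
| Plus discontinuers' follow-up at L + 14, mapped by window | −3.79 to −3.95 | 0.03 to 0.20 |
| Plus combined visit at Day 92, mapped by window | −3.36 to −3.82 | 0.16 to 0.61 |

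About 0.5 to 2 people per arm of 50 are affected under L + 14 mapping, and about 4 to 9 under the combined visit. With no off-drug regain at all, the three discontinuer readings still shift the estimate by 0.03 to 0.41. Across those readings the shift is 0.01 to 0.30 at 10% drop-out and 0.04 to 0.93 at 30%.

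A separately built simulation (20,000 per arm; assumed SDs of 2, 3 and 4.2 at Weeks 4, 8 and 15; correlations 0.60 to 0.95; stopping uniform over Days 1 to 90) gave 3.99 to 4.04 with or without completers' Week 15 weights. With discontinuers' follow-up included (at Day 105 or L + 14) and with regain, it gave 3.65 to 3.93 at 20% drop-out in both arms and 3.47 to 3.86 at 10% placebo, 30% active. With no regain it gave 3.51 to 3.95 over both drop-out patterns.

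**Single trials.** In 400 runs of 50 per arm (half-life 28 days, half of stops early, full attendance), combined-visit mapping moved the estimate by a mean of 0.52 (5th to 95th percentile 0.04 to 1.12). L + 14 mapping moved it by 0.07 (−0.10 to 0.27). The SD of the estimate was 0.82.

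**Power in the worst case.** Φ(3.36/0.894 − 1.96) = Φ(1.80) = 0.96.

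**The case against.** The strongest reply is that completers only is what was meant. The sentence begins with participants taking randomized treatment, a scheduled follow-up most naturally means the Week 15 visit, and SAP 5.8.1.3 names retrieved dropouts only for the secondary estimand. On that reading the shift is zero. This is a fair account of the probable intent, but 5.8.1.2 does not say it, and a primary analysis should not depend on inferring it.

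Second, the windows only label visits; they do not decide which records enter the model. SAP 5.1.6 also says that no windows apply to scheduled visits. That bears on the mapping to Week 13, but the same section expressly windows discontinuers' follow-up visits and exempts no analysis. Even unmapped, as a separate Week 15 level, these weights move the estimate by 0.05 to 0.31.

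Third, the largest figures come from the combined visit, which is optional. That weight is also an end-of-treatment weight, which the 3-day rule would exclude. This stands: 0.16 to 0.61 is the least likely route. The protocol's default for discontinuers is to keep the schedule, so the separate Week 15 range is the more natural one.

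Fourth, the per-protocol comparison concerns Week 13 weights in a different analysis set. It shows the SAP's general attitude and no more.

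Finally, the programming specifications are in a separate document and may settle the point. They do not replace a statement in the SAP.

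**Conclusion.** The concern holds. The ambiguity and the undeclared departure are plain on the page: section 8 is wrong on any reading, because both the 3-day extension and the follow-up clause are absent from the protocol.

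The bias is conditional. It is zero if only completers' Week 15 weights are added as their own visit level. It is about 0.03 to 0.61 points out of 4.0, toward zero, if discontinuers' follow-up weights enter at 20% drop-out. In a single trial under L + 14 mapping the sign is not assured. Power is not threatened, and attenuation is conservative for a superiority claim.

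The size rests on assumptions that the documents do not supply: regain half-life of 14, 28 or 56 days or none; 50% or 100% attending follow-up; 50% or 100% weighed within 3 days of stopping; stopping times uniform or half in the first 28 days; linear accrual; and drop-out unrelated to weight. The first simulation kept on-treatment weights whenever two fell in one window. SAP 5.1.6 ranks by visit category and then nearness to the target day, so the mapped figures may be somewhat low.

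This should be fixed before database lock.

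**What to change.** - **SAP 5.8.1.2:** delete the follow-up clause for the primary estimand, or restrict it to completers' Week 15 weight as a separate visit level, and state which. Add that for discontinuers no weight taken more than 3 days after the last dose enters this analysis or is mapped to Week 4, 8 or 13, including one from a combined end-of-treatment and end-of-trial visit.
- **SAP 5.1.6:** state that mapping of off-drug follow-up weights serves the treatment-policy analysis in 5.8.1.3, which keeps all of them.
- **SAP section 8:** record the 3-day extension, and completers' Week 15 data if retained, as departures from Protocol 16.6.1.

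The cost is SAP wording and one data-selection flag before database lock. No new data and no protocol amendment are needed.
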